**2. \* Study Title:**

Effect of a 9-Month Internship Intervention for Military Dependents with ASD

**3. \* Is this a student or trainee project in which activities will be carried out by that individual under your supervision (for example, dissertation or degree-required projects):**

Yes

No

**4. \* Please select the primary department or center that this study is being conducted under:**

SOE Spec Ed and DP RRTC

**7. \* Select one of the following that applies to the project (selection will branch to new pages):**

*Note: VCU IRB offers guidance for many types of studies, including secondary data analysis studies, internet research, registries, EFIC, HUD, and Emergency Use protocols.*

See [https://research.vcu.edu/human\\_research/guidance.htm](https://research.vcu.edu/human_research/guidance.htm)

Research Project or Clinical Investigation [\*most exempt, expedited, and full board research studies]

Exception from Informed Consent (EFIC) for Planned Emergency Research

Humanitarian Use of Device for Treatment or Diagnosis

Humanitarian Use of Device for Clinical Investigation

Emergency Use of Investigational Drug, Biologic or Device

Treatment Use (Expanded Access to Investigational Product for Treatment Use)

Center or Institute Administrative Grant Review

Request for Not Human Subject Research Determination (i.e. request a letter confirming that IRB review is not required)

## Federal Regulations

1. \* Is this a FDA regulated study?

FDA regulated research includes all clinical investigations involving a test article and a human subject(s) that has been submitted for approval to the FDA or may be submitted in the future.

Check Yes if

- the study involves an IND/IDE, abbreviated IDE, IND/IDE exemption, HUD, expanded access, or is otherwise subject to 21 CFR 56,
- the study involves a test article being administered or dispensed to subjects NOT according to a clinicians' medical judgment but rather, per the study protocol, OR
- the study does not involve a test article but intends to provide safety or efficacy data to the FDA.

Yes

No

2. \* Is this study supported by the Department of Defense (DoD):

Yes

No

3. \* Specify which component(s) of the DoD supports this research:

Army

Navy/Marine Corp

Air Force

National Security Agency

National Geospatial Intelligence Agency

4. \* Check if any of the following funding sources apply to this research (including Direct and/or Indirect funding):

Department of Education

Department of Justice

Environmental Protection Agency

None of the above

## IRB Panel Setup

1. \* To which IRB is this study being submitted for review?

- VCU IRB
- WCG IRB
- NCI Central IRB
- Advarra IRB
- Other IRB

2. \* Is this study transitioning to review by another IRB?

- Yes - transitioning from VCU IRB to an external IRB (WCG, CIRB, Other)
- Yes - transitioning from an external IRB (WCG, CIRB, Other) to VCU IRB
- No or not applicable

## Review Setup

1. \* Select which study type best describes the majority of the study. Your response will help determine which IRB panel should review this.

Bio-Medical Research  
 Social/Behavioral/Education (SBE) Research

2. \* Which option(s) best describe the way(s) this study's procedures will be conducted? (Select all that apply.) This information may be used by the IRB in triaging studies during an emergency.

In-person interactions / interventions with participants  
 Remote interactions / interventions with participants  
 Secondary data/specimen analyses with or without contact with study participants

3. \* Would it be possible to convert in-person activities in your study to remote if there is an approved contingency protocol?

Yes, could convert to remote activities

4. \* Does this study involve greater than minimal risk:

Yes  No

5. \* Review type requested: (subject to IRB approval):

Full Board  
 Expedited  
 Exempt

6. \* Is this study initiated by a VCU investigator or a sponsor:

VCU Investigator initiated  
 Sponsor or industry initiated

The IRB has determined that the selected types of anticipated individual and social benefit apply to this study

The below information is read-only to investigators, and the categories are set by the IRB during review. All categories will appear blank until the IRB has made a determination. If a category is not checked, it does not apply to this study. This information may be used by the IRB in triaging studies during an emergency situation.

Possible or minimal direct benefit to the community

Scientific benefit

The following information applies to studies being reviewed by the VCU IRB.

The IRB has determined that the selected Exempt and/or Expedited categories apply to this study.

The below information is read-only to investigators, and the categories are set by the IRB during review. All categories will appear blank until the IRB has made a determination. If a category is not checked, it does not apply to this study or the study is being reviewed by an external IRB.

**7. For Expedited Studies:**

Category	Nonresearch Data	Involves materials (data, documents, records, or specimens) that have been collected or will be collected solely for nonresearch purposes including medical treatment or diagnosis.
5	Collection	
Category	Research Data	Involves the collection of data from voice, video, digital, or image recordings made for research purposes.
6	Collection	
Category	Behavioral	Is research that will be performed on individual or group characteristics or behavior OR will employ a survey, interview, oral history, focus group, program evaluation, human factors evaluation, or quality assurance methodologies.
7		

## Initial Setup Complete

Protocol Progress:

- **INITIAL SETUP**
- ② BACKGROUND, RATIONALE & GOALS
- ③ RESEARCH PLAN
- ④ CONSENT PLAN
- ⑤ RISKS, PRIVACY & CONFIDENTIALITY
- ⑥ POPULATIONS WITH SPECIAL CONSIDERATIONS
- ⑦ INSTITUTIONAL REQUIREMENTS
- ⑧ DOCUMENTS

Click Continue below to go to the next section

## Background, Rationale and Goals

**1. \* Describe the study's background and what is currently known from the scientific literature, including citations, or upload a citation list in document upload. Use lay language whenever possible.**

Individuals with Autism Spectrum Disorders (ASD) who graduate from high school seeking employment face significant challenges compared with those with other disabilities. Shattuck et al. (2011) noted that nearly 80% still live at home, almost half have no job or post-secondary training, 40% do not have contact with friends, 17% do not feel hopeful about their future, 21% do not engage in outside activities, and many experience a decrease in insurance coverage and access to therapy services. Additionally, individuals with ASD in adolescence and early adulthood have a higher incidence of anxiety disorders, including obsessive compulsive disorder, and depression than their peers without disabilities or other disabilities (Gotham, Brunwasser, & Lord, 2015). The lack of access to services and poor outcomes along with an apparent fragile mental health frequently may lead to social isolation, increasing the fragility of the individual (Bishop-Fitzpatrick, Mazefsky, Minshew, & Eack, 2015; Swain, Scarpa, White, & Laugeson, 2015). Thus, transition service providers, including educational and vocational rehabilitation service providers are struggling to meet their responsibility to prepare students with ASD for productive and independent lives after high school. At the same time, however, the blame for this condition does not rest entirely with teachers, job coaches, and vocational rehabilitation case managers. The research community bears significant responsibility for this dilemma by failing to include transition-aged high school students with ASD in meaningful research to determine practices that will reverse this trend. Military dependents with ASD in the 18-22 year old (transition) age ranges are further disadvantaged by a total lack of clinical research addressing their unique needs. Thus the proposed study fills an important clinical practice and research gap. Specifically, the proposed project will study the impact of a transition to employment model, Project SEARCH plus ASD Supports (PS+ASD), which has evidence of efficacy for increasing employment outcomes and independence in 18-22 year olds with ASD. The proposed project will extend previous work by exploring the impact of PS+ASD for military dependents with ASD while also measuring the impact of the intervention on social responsiveness, mental health, and quality of life.

In this project, we target 18-22 year old military dependents with ASD in their final year of high school as they transition to employment. The United States General Accountability Office noted that improved transition practices and outcomes for youth with disabilities is a major need (United States Government Accountability Office, July 2012). Young people with ASD present unique challenges related to post school employment outcomes. Community based employment rates for individuals with ASD, regardless of intellectual ability, reportedly range between 4.1 to 11.8% (Taylor & Seltzer, 2011). Across the ability spectrum, individuals with ASD have lower rates of participation in vocational or technical education, employment, and post-secondary education in 2 or 4-year programs than their peers with speech language impairments, learning disabilities or intellectual disabilities for as long as 7 years post high school. ([name], Targett, & [name], 2013; Shattuck et al., 2012).

Additionally, adolescents and young adults with ASD largely have been orphaned from the research literature addressing transition from high school to employment. A review of the extant literature on interventions for individuals with ASD reveals a paucity of research regarding transition packages and models that would change this pattern of significant underperformance in the transition to adulthood and incorporate autism specific interventions (e.g., [name], Carr, Targett, West, & [name], 2014; [name], Targett, & [name], 2013; Shattuck, et al., 2012). Most of the existing literature has described the characteristics of transition-aged young adult population of individuals with ASD, the services or lack thereof that young adults with ASD access or the poor outcomes achieved by this group of individuals (e.g., Barker, et al., 2011; Cimera & Cowan, 2009; Henninger & Taylor, 2012; [name] & [name], 2010; Shattuck, et al., 2010; Shattuck, et al., 2012; Smith, Fleming, Wright, Losh, Hamm, Olsen, & Bell, 2015). The findings from this literature indicate that, despite a slight lessening of the original symptoms, individuals with ASD continue to have significant challenges in all environments related to social interaction, communication, and independence into adolescence and adulthood.

Military dependents with ASD who are transitioning from school to employment experience greater disadvantages than their non-military peers with ASD. For example, relocation and deployment in service to our nation may unwittingly trigger many of the conditions associated with poor transition outcomes for youth with ASD. Specifically, life in the military may lead to increased stress, lower social skills, and increased maladaptive behavior for the individual with ASD. Additionally, due to frequent moves, the family may lack access to local resources to support the individual with ASD (Lincoln & Sweeten, 2011). Finally, there have been no research intervention studies to explore treatment models targeted to transition aged military dependents with ASD.

By subjecting PS+ASD to the rigor of a clinical trial with military dependents with ASD, we expect to expand the model to include essential elements to meet the needs of this population of individuals who may be dually disadvantaged by their disability and their status as military dependents. Such information may lead to the development of improved outcomes for these individuals and reduce stress for their families.

**2. \* Describe the study hypothesis and/or research questions. Use lay language whenever possible.**

There are three primary and three secondary endpoints under investigation in this study: (1) Employment status, (2) wage, (3) number of hours worked per week at 12 and 18-months post enrollment. In addition, the effect of the intervention on (5) social communication, (6) mental health, and (7) quality of life will be explored. Specifically, our hypotheses are:

Hypothesis 1: Young adults who participate in an employer-based employment training and placement program will demonstrate a higher rate of employment than those in the control condition.

Hypothesis 2: Young adults who participate in a work-based employment training and placement program will earn higher wages on average compared to those in the control condition.

Hypothesis 3: Young adults who participate in a work-based employment training and placement program will work more hours per week on average than those in the control condition.

Hypothesis 4: Young adults who participate in a work-based employment training and placement program will increase their social responsiveness skills compared to those in the control condition, as measured by the Social Responsive

Scale, 2nd Ed.

Hypothesis 5: Young adults who participate in a work based employment training and placement program will display lower anxiety and depression scores than those in the control condition as measured by the Behavior Assessment System for Children, 3rd Ed. Teacher Rating Scales – Adolescent version.

Hypothesis 6: Young adults who participate in a work based employment training and placement program will report higher quality of life scores than those in the control condition as measured by the Quality of Life Questionnaire.

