**3. \* Describe the study's specific aims or goals. Use lay language whenever possible.**

The objective of this proposed project is to study the impact of Project SEARCH plus Autism Spectrum Disorders Supports (PS+ASD) on the social communication, behavioral, and employment outcomes of military dependents with ASD using a randomized clinical trial with a wait-list control group. We propose to implement an efficacious intervention, PS+ASD, for 18 – 22 year old military dependents with ASD, to measure the effect of this intervention on community-based competitive employment, social communication, mental health, and quality of life. The primary objective of this research is to determine if subjects who receive PS+ASD have greater improvement in three vocational domains (employment status, wage, number of hours worked per week) than subjects in a wait-list control group at 12 and 18 -months post-enrollment.

Secondary Objectives. To assess differences in three personal domains (social communication, mental health, and quality of life) for the treatment and wait-list control groups at baseline, 12 and 18-months post enrollment.

Exploratory Objectives. Exploratory objectives are to compare the three vocational domains and three personal domains at baseline, 12 and 18-months post enrollment in subjects receiving the treatment compared to those in the wait-list control group.

Aims. The aims of this project are to (1) Modify PS+ASD Model for Military Dependents, (2) implement the intervention based upon the PS+ASD manual with the addition of the modified elements and will measure fidelity of implementation, (3) measure the impact of the intervention on the employment outcomes social communication, mental health and quality of life of the military dependents who participate compared to an equal control group who do not receive the intervention.

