**5. \* Describe any potential for direct benefits to participants in this study:**

We anticipate numerous positive outcomes from this project. At a minimum, 38 youth with autism will engage in community-based work experiences that lead to a competitive employment job while transitioning from school to adulthood. There is no guarantee of direct benefit to all individual participants.

The control group participants will benefit from participation in the assessments during the research. By completing the Supports Intensity Scale, they will gain a better understanding of their skill development needs with respect to future employment.

**6. \* Describe any potential for direct social impact in this study . For example, any engagement with specific communities to respond to community-identified needs, or ways the study will strengthen the well-being of the specific communities if applicable:**

This study resulted in a significantly higher percentage of participants in the PS+ASD condition acquiring employment while participants who were initially assigned to the waitlist condition were unlikely to acquire employment. Further, the acquisition of employment was demonstrated to result in higher rates of independence and quality of life outcomes for participants who gained employment. This represents both an important research outcome and a critical outcome for military dependent and connected youth. This is also an important study for military families as they navigate the complexities of military life (frequent moves, wait lists for services, etc.) and supporting a youth with autism.

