**4. \* List the study inclusion criteria:**

In order to be selected for inclusion in the sample pool, participants must meet the following criteria: (1) A diagnosis of Autism Spectrum Disorder; (2) between 18 - 22 years of age; (3) entering final year of school participation and is on track to receive a diploma or a certificate; (4) meets eligibility requirements for vocational rehabilitation; (5) possesses independent personal hygiene, eating and grooming skills; (5) able to pass drug screen and felony check and have immunizations up to date (These items will be seen by the community business only as required by them for interns to be present at their work site); and (6) desires and plans to work competitively in the community at the conclusion of the 9-month program, (7) Be a military dependent or military connected youth.

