**3. Eligibility screening prior to consent and how those activities will be carried out (when applicable)**

**See the help text for additional guidance.**

Students will be recruited through their schools through (a) a flyer advertising an informational meeting for students and parents with information about the study; (b) a letter to students and parents sent by the school, and (c) regularly scheduled Individualized Education Plan (IEP) meetings at which parents and students attend. Information about the study will be provided to students and to their families.

Potential participants will submit an application that contains their contact information. (See Application for Participation located in the recruitment materials sections).

Recruitment activities will be held from January through May of years 1 and 2. Recruitment may occur in year 3 if there is significant attrition of participants. Once all participants are enrolled and identified, we will assign a number to each enrolled participant and complete randomization using a random numbers generator on a computer. The individual completing randomization will not know the identity or group to which individuals are assigned.

Recruitment procedures will be completed as follows:

1. Each school district representative who participates on the coordinating team will schedule an informational meeting in their school division for potential participants from their schools.
2. Applications and flyers announcing informational meetings will be sent to all school district representatives to share with potential participants in January of years 1, 2, and potentially 3.
3. Informational meetings will be held at the times and in the locations identified by the school district representatives.
4. If potential participants or their family members are unable to attend the informational meetings, VCU staff will meet with them at a time and location of their choosing.
5. At each informational meeting, potential participants and their family members will receive an application with instructions on how to apply, when and where to deliver completed applications.
6. VCU staff will answer any questions from potential participants regarding the research.
7. Upon receipt of the application, VCU staff will coordinate with the screening team to schedule screening interviews in a private location that is convenient to the potential participant and their family members.

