**See the help text for additional guidance**

This is a randomized, wait-list controlled study of the efficacy of the Project Search plus ASD Supports Model (PS+ASD) in 32 adolescents and young adults aged 18 to 22 with ASD. Approximately 32 subjects will be enrolled and randomized in a 1:1 ratio to treatment or wait-list control. A sufficient number of potential subjects will be screened to achieve this number of enrolled subjects.

The six dependent variables in question are the primary endpoint employment rate (upon completion and at 12 months and 18 months post-enrollment) and the secondary endpoints hourly wages, hours/week, Social Responsiveness Scale total score, Behavior Assessment System for Children 3rd Ed. Anxiety and Depression t-score and the Quality of Life Questionnaire percentile score at baseline (Baseline), 12 months post enrollment (12 months), and 18 months post-enrollment (18 months). The efficacy of the intervention will be analyzed by comparing the differences in these six variables between the treatment group and the control group.

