
Project SEARCH is an intensive 9-month job training program where youth with developmental disabilities in their last year of high school are embedded in a large community business such as a hospital, government complex, or banking center where they rotate through three 10-12 week internships within the business. Subjects will log approximately 720 hours of internship time learning marketable skills and 180 hours of business site classroom time learning social communication and adaptive behavior for a total of approximately 900 hours embedded in the business setting. In order to meet the unique needs of youth with ASD, [name], et al. enhanced the Project SEARCH model by adding autism supports to the original model. Those added supports were: 1) on-site, intensive, systematic instruction using the principles of applied behavior analysis, 2) on-site support and consultation from a behavior/autism specialist, and 3) intensive staff training in ASD and the Project SEARCH Model. This resulted in PS+ASD. It is the impact of this intervention for military dependents with ASD we will assess through this project.

As a part of this study, we will collect the following educational records:

1. The Individualized Education Plan for each student.
2. The student's attendance record to assess the student's fitness to participate in the study
3. The student's transcript to insure eligibility for the study
4. The student's prior work/study history for demographic information

5. Any prior career assessment information to assist in understanding the student's job training desires and needs.

Participation in this study will not be considered a part of the credits a student needs to complete graduation requirements.

We have submitted and received approval for our research protocol from the Human Research Protection Office of the DoD.

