## Behavioral Intervention/Task Details

This page asks for details about the social/behavioral intervention, task, or environmental manipulation in the research.

Interventions include both physical procedures by which information is gathered and manipulations of the subject or the subject's environment that are performed for research purposes. This might include activities such as playing computer games, performing a task, thought/cognition activities, environmental manipulations, and educational activities.

If the study only involves surveys, interviews, or secondary data collection, go back to the Project Details page and uncheck "Social/Behavioral interventions or experimentation / Tasks / Environmental manipulations" in Question 1.

- 1. \* Describe the duration of the social/behavioral intervention, task, or environmental manipulation:**  
The Project SEARCH + ASD Supports intervention is a 9-month intervention.

- 2. \* Describe any potential harms or discomforts that participants could experience during the intervention activity:**  
The only potential harm or discomfort participants might experience is possible loss of confidentiality.

- 3. \* Will the intervention activity be physically invasive or painful?**

Yes

No

- 4. \* Describe the impact the intervention activity will have on participants, including the nature and duration of any impact(s):**

The potential impact of the intervention is that participants may acquire employment upon completion of the intervention. The nature of that impact is desirable and the duration of employment may vary depending on the participant's needs and abilities.

- 5. \* In the investigator's opinion, is there any reason to think that the participants will find the intervention activity offensive or embarrassing? Explain why or why not.**

We do not believe the participants will find the intervention offensive or embarrassing. We have concluded this because we have tested this intervention in other locations and no participants have reported feeling embarrassed or offended by the intervention. We also work with participating intervention sites to educate them regarding the needs and abilities of youth and young adults with ASD. Finally, we provide on-going support to participants and the sites to ensure that participants receive support in their participation to avoid embarrassing or offensive situations.

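### Hypothesis 5 relies on a teacher-completed form at 18 months, when treated participants have probably left school and control status is unresolved

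*Combined protocol and SAP*

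**What the plan says.** Background, Rationale and Goals Q2 and Study Procedures Q1 define Hypothesis 5 on anxiety and depression "as measured by the Behavior Assessment System for Children, 3rd Ed. Teacher Rating Scales" (Adolescent version). The only BASC-3 form in the list of uploaded documents is the teacher form.

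Study Procedures Q6 lists the BASC-3 anxiety and depression t-score among the outcomes measured "at baseline (Baseline), 12 months post enrollment (12 months), and 18 months post-enrollment (18 months". The secondary objectives (Background Q3, repeated in Study Procedures Q2) give the same three times for the mental-health domain.

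Study Population Q4 requires each participant to be "entering final year of school participation and is on track to receive a diploma or a certificate". Study Procedures Q6 places the programme in the same year: "youth with developmental disabilities in their last year of high school are embedded in a large community business". Behavioral Intervention/Task Details Q1 gives its length: "The Project SEARCH + ASD Supports intervention is a 9-month intervention". On recruitment, Study Procedures Q4 says: "Recruitment activities will be held from January through May of years 1 and 2".

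Study Population Q3 expects 20 teachers as informants for 38 participants but does not assign them to visits. Educator consent is taken when the measures are first reviewed with the educator. The one substitute-respondent rule, in Study Procedures Q6, lets a parent or guardian answer when the participant cannot. It does not cover an absent teacher.

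The comparator is called a wait-list control. The aims, however, describe a comparison "compared to an equal control group who do not receive the intervention", while Background Q6 says that "participants who were initially assigned to the waitlist condition were unlikely to acquire employment". No crossover date is given.

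**The concern.** A teacher rating needs a teacher who sees the participant. The plan recruits people about to begin their last school year and then asks for a teacher rating a year and a half after enrolment. If school has ended by then, the 18-month score is either missing or recalled by someone who no longer has contact. Neither is the measurement taken at baseline.

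This is separate from whether the teacher knows the allocation. A fully masked teacher would have the same problem.

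Two things are at stake for this secondary outcome. The first is precision, because the 18-month contrast shrinks with each rating lost. The second is bias. If some wait-listed controls later entered the programme, which the personnel section says is delivered in part by a school-division teacher, they could have a current teacher at 18 months when treated participants do not. Whether a score exists, and the setting it describes, would then depend on arm.

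**Working it through.** **Calendar check**

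Inputs from the documents: recruitment January to May (Study Procedures Q4); final school year begins after entry (Study Population Q4); visits at 12 and 18 months post enrolment (Study Procedures Q6). Assumptions: the final school year ends about June of year Y+1, and participants leave school then. The documents give no school calendar and do not say which date counts as enrolment, so both plausible time zeros are shown.

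Number the months from January of year Y as 0, so that June of Y+1 is 17. For calendar month e of year Y and a visit at k months, months after school ends = (e − 1) + k − 17.

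| Time zero | 12-month visit | 18-month visit |
|---|---|---|
| January Y | 0 + 12 − 17 = −5 (in school) | 0 + 18 − 17 = +1 (July) |
| May Y | 4 + 12 − 17 = −1 (in school) | 4 + 18 − 17 = +5 (November) |
| August Y | 7 + 12 − 17 = +2 | 7 + 18 − 17 = +8 (February Y+2) |
| September Y | 8 + 12 − 17 = +3 | 8 + 18 − 17 = +9 (March Y+2) |

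February to April give +2 to +4 at 18 months. Under every time zero tested, the 18-month visit falls after school ends. The 12-month visit is in school for January to May and out of school for August or September. A year-end one month earlier adds 1 to each figure; one month later subtracts 1, which takes the January figure to 0.

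**Precision, for illustration**

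The plan's figure comes first. Study Population Q3 states power 0.85 (95% CL 0.81 to 0.88) for d = 1.10 with 16 per arm at alpha 0.05, using a mixed model with three time points. A simple two-sample t calculation, two-sided, has df = 2n − 2 and noncentrality d / √(2/n). With n = 16, 1.10 / √(2/16) = 3.11 on 30 df, and power is 0.853. The stated figure is reproduced.

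The same formula for a single 18-month comparison, if only some participants can still be teacher-rated (the shares are assumptions):

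| Rated per arm | Noncentrality | df | Power |
|---|---|---|---|
| 16 (100%) | 3.11 | 30 | 0.85 |
| 12 (75%) | 2.69 | 22 | 0.73 |
| 8 (50%) | 2.20 | 14 | 0.54 |
| 4 (25%) | 1.56 | 6 | 0.26 |

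If an arm has no ratings, the 18-month teacher-rated contrast cannot be estimated from observed data.

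**Control arm**

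The final-year criterion and the aim "compared to an equal control group who do not receive the intervention" imply that controls leave school on the same calendar as treated participants. The wait-list label and "participants who were initially assigned to the waitlist condition were unlikely to acquire employment" allow later entry to a programme with a school teacher on its staff. The text does not choose between them.

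**The case against.** The strongest reply is that none of this is stated outright. The plan gives no school calendar, no definition of the enrolment date and no rule that the rater must have current contact. For a January enrollee, a teacher who saw the participant about a month earlier could still complete the form. That is a recall weakness rather than an impossible measurement. Several documents that could hold a rater rule are listed but not reproduced here: the data collection instruments attachment, the 12 and 18 month script and the educator consent. The outcome is secondary, and a mixed model with three time points can use participants with incomplete follow-up if data are missing at random.

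Much of this stands as a limit on size. A reader might infer that no teacher exists in either arm, that the 18-month score cannot be obtained, or that all of it is lost. The documents do not support those readings. The inference is firm for treated participants only, control status is open, and a retrospective rating is conceivable.

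What remains is that the visible text asks for a teacher rating after the probable end of school and provides no substitute. The mixed model does not cure this. Baseline, and on the January to May reading 12-month, ratings still inform Hypothesis 5. But the 18-month contrast would rest on whoever happened to have a rater, and that could depend on arm.

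**Conclusion.** The point holds in a limited form and should be corrected. Assuming a school year ending about June, the 18-month teacher rating falls about 1 to 5 months after school ends with a January to May time zero. With a start-of-school time zero it falls about 8 to 9 months after, and the 12-month visit is then also 2 to 3 months late. Treated participants would therefore probably lack a current teacher at 18 months. Whether controls do is unresolved, so rater availability could differ by arm.

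The share of ratings that would be lost cannot be derived from the documents; the power figures above show only what assumed losses would cost. It would also be tempting to say that a parent could simply step in because parents are at every visit. The documents show parents as consented participants who answer case by case. They do not place parents at all visits, and no parent BASC-3 form is listed. The consequence is confined to Hypothesis 5; the primary employment endpoint is not affected.

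**What to change.** Define the date that counts as enrolment. Limit the teacher-rated between-arm test for Hypothesis 5 to the last visit at which both arms are in school, and label any 18-month teacher rating descriptive. With a January to May time zero, that visit is the 12-month one. With a start-of-school time zero, neither scheduled follow-up qualifies, and an assessment before the school year ends would have to be added.

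Amend the BASC-3 timing in Study Procedures Q6 and the mental-health timing in the secondary objectives (Background Q3, Study Procedures Q2), and reconcile both with the wait-list timing. The hypothesis lists (Background Q2, Study Procedures Q1) attach 12 and 18 months to the vocational endpoints only, so their timing need not change. State how a missing teacher rating is handled.

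The cost is mainly wording and the loss of a confirmatory 18-month teacher-rated contrast.

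If an 18-month comparison for Hypothesis 5 is wanted, use one informant type from baseline onward in both arms, for example a parent form. That costs more: a new instrument, attendance that must be written into each visit, an informant who knows the allocation, and pilot effect sizes that may not carry over to the new rater.
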